# **Clinical Study Protocol**

## **Johnson & Johnson Vision Care, Inc.**

NIBUT or lower TMH, on average, for symptomatic subjects compared to asymptomatic subjects after 14 hours of lens wear will be concluded if the upper limit of the 95% confidence intervals for the Least-squares means is less than 0.

### **Tear Film Osmolarity (TOSM)**

TOSM will be analyzed using a linear mixed model by adjusting the baseline TOSM as a covariate. The model will include subject strata (asymptomatic/symptomatic), time event (i.e., fitting and 14-hours follow-up), and strata by time event interaction as fixed effects; subject will be included as random effects (G-side). Other characteristics such as age, gender, and race will be included as fixed covariates when appropriate. Different covariance structures will be considered to model the residual errors between the repeated measurements within time event from the same subject (R-side). The covariance structure will be selected based on the finite-sample corrected Akaike's Information Criterion. The following covariate structures will be considered:

- Unstructured Covariance Structure (UN)
- Homogenous Compound symmetry (CS)

The structure that returns the lowest Akaike Information Criteria Corrected (AICC) will be selected as the structure that best fit the data. Heterogeneous covariance structures across strata may be considered if necessary. The Kenward and Roger method (Kenward and Roger, 1997) will be used for the denominator degree of freedom.

Comparisons between subject groups for TOSM will be carried out using a one-sided 95% CI of least-square means differences (symptomatic - asymptomatic) at 14-hour follow-up for the hypothesis given below:

$$\begin{aligned} H_0: \mu_S - \mu_A &\leq 0 \\ H_A: \mu_S - \mu_A &> 0, \end{aligned}$$

where S=Symptomatic and A=Asymptomatic. No multiple adjustment will be necessary since the hypothesis test will be conducted based on only 14-hour follow-up. A statistically greater TOSM, on average, for symptomatic subjects compared to asymptomatic subjects after 14 hours of lens wear will be concluded if the lower limit of the 95% confidence intervals for the Least-squares means is greater than 0.

### **Number of White Blood Cells (WBC)**

The number of white blood cells (visualized by confocal microscopy) after 6-hour follow up will be analyzed using a generalized linear mixed model with Poisson distribution and log link function. The model will include subject strata (asymptomatic/symptomatic) as fixed effects; subject will be included as random effects (G-side). Other characteristics such as age, gender, and race will be included as fixed covariates when appropriate. Different covariance structures will be considered to model the residual errors between the lower and upper lid margin measurements within eye from the same subject (R-side). The covariance structure will be selected based on the finite-sample corrected Akaike's Information Criterion. The following covariate structures will be considered:

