# Clinical Study Protocol

## Johnson & Johnson Vision Care, Inc.

Study Endpoints	
Primary endpoints: Lid margin staining grade, NIBUT, TMH, tear film osmolarity, mean density of white blood cells
 
Secondary endpoints: VAS comfort scores
 
Other endpoints: Change from baseline, change from fitting, CLDEQ-8 and change in CLDEQ-8

Study Design	
This is a 2-Part, 8-Visit, single-center, open-label, bilateral and dispensing clinical study. In Part 1 (Visits 1-4) all subjects will be dispensed Dailies AquaComfort Plus, in Part 2 (Visits 5-8) all subjects will be dispensed Acuvue Oasys 1-Day.
 
Part 1            Approximately 210-240 subjects will be recruited and fitted with Dailies AquaComfort Plus over approximately a two-week period in order to identify ~27 asymptomatic (CLDEQ-8 score less or equal to 10) and ~27 symptomatic (CLDEQ-8 score more than or equal to 20). Only those subjects classified as asymptomatic or symptomatic at the end of Visit 2 (~54 subjects) will be asked to continue. Visits 3 and 4 will take place in the early morning and after <math>14 \pm 2</math> hours respectively, on a single study day.
 
Part 2            Subjects who complete Part 1 (~ 54 subjects) will continue onto Part 2. The visit procedures will be the same as for Part 1 but subjects will use the Acuvue Oasys 1-Day lens.
 
See the flow chart at the end of the synopsis table for the schematic of the study visits and procedures of main observations (Figure 1)

Sample Size	Part 1, Visits 1 & 2: ~210-240 subjects Part 1, Visits 3 & 4: ~54 subjects Part 2: ~54 subjects
Study Duration	The study will last approximately 18 months and will include a 9-month recruitment period.
Anticipated Study Population	Habitual soft contact lens wearers aged 18-45 years will be stratified into asymptomatic and symptomatic lens wearers based on their CLDEQ-8 score.

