### **2.2. Endpoints**

Primary Endpoint(s)

The primary endpoints in this study are lid margin lissamine green staining grade, NIBUT, TMH, tear film osmolarity at the beginning and the end of a lens-wearing day (after 14 hours). Additionally, the number of white blood cells in the lid margins after 6 hours of lens wear will be investigated.

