### White Blood Cells (mean density of cells)

Images, using Confocal Microscopy will be taken in both eyes for both the upper and lower eyelid in the central lid area. These images will be used to determine the density of inflammatory white blood cells.

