### **2.3. Hypotheses**

Primary Hypotheses

For Part 1:

1. Symptomatic subjects will have, on average, statistically significantly, greater upper and lower lid margin staining compared to asymptomatic subjects after 14 hours of lens wear.
2. Symptomatic subjects will have, on average, statistically significantly, shorter NIBUT compared to asymptomatic subjects after 14 hours of lens wear.
3. Symptomatic subjects will have, on average, statistically significantly, lower TMH compared to asymptomatic subjects after 14 hours of lens wear.
4. Symptomatic subjects will have, on average, statistically significantly, greater tear film osmolarity compared to asymptomatic subjects after 14 hours of lens wear.
5. Symptomatic subjects will have, on average, statistically significantly, greater density of white blood cells (visualized by confocal microscopy) in both the upper and lower lid margins compared to asymptomatic subjects after 6 hours of lens wear.

Secondary Hypotheses:

For Part 1 and 2

1. There is a statistically significant relationship with at least one of the five clinical measures (lid margin staining, NIBUT, TMH, tear film osmolarity and density of white blood cells) and subjective comfort measured using VAS grading scales at 14 hours (6 hours for white cells).

Other Hypotheses:

For Part 2:

1. Symptomatic subjects will have, on average, statistically significantly, greater upper and lower lid margin staining compared to asymptomatic subjects after 14 hours of lens wear.
2. Symptomatic subjects will have, on average, statistically significantly, shorter NIBUT compared to asymptomatic subjects after 14 hours of lens wear.
3. Symptomatic subjects will have, on average, statistically significantly, lower TMH compared to asymptomatic subjects after 14 hours of lens wear.
4. Symptomatic subjects will have, on average, statistically significantly, greater tear film osmolarity compared to asymptomatic subjects after 14 hours of lens wear.

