**Clinical Study Protocol**  
**Johnson & Johnson Vision Care, Inc.**

Visit 2: Treatment 1 Follow-Up (after two weeks)		
Step	Procedure	Details
2.7	Subjective comfort	
Subjective comfort scores using a vertical VAS scale will be recorded for the following for each lens (OD and OS):
 
Comfort just after lens application over the two week period
 
Comfort just before lens removal over the two week period

2.8	LogMAR visual acuity & over-refraction	Distance high contrast visual acuity will be measured for each eye and binocularly before and after over-refraction.
2.9	Lens fitting and surface assessment	
Lens fit will be recorded for each of the following criteria: horizontal centration, vertical centration, movement and coverage.
 
The lens surface will be recorded according to the following integer scales: lens deposits (0-2), deposit degree (0-4), lens debris (0-4) and lens wettability (0-4).

2.10	Lens removal	Lenses will be removed and discarded.
2.11	Confocal microscopy (ONLY subjects who are classified as asymptomatic or symptomatic)	
Confocal microscopy will be undertaken in the following areas:
 
OD and OS Central upper lid margin
 
OD and OS Central lower lid margin
 
A number of images will be undertaken across the central lid area. Image analysis will be subsequently undertaken in order to determine the number of white blood cells.

2.12	Slit lamp biomicroscopy	
Grades will be scored to the nearest 0.1 in the best judgment of the investigator using Efron Grading Scales.
 
N.B. For subjects who are NOT classified as asymptomatic or symptomatic slit lamp biomicroscopy will take place as part of the final evaluation form.

2.13	Continuance	
For a subject to continue on the study they must meet the following criteria:
 
Their CLDEQ-8 score must be either <math>\leq 10</math> (to be classified as asymptomatic)

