# Clinical Study Protocol

## Johnson & Johnson Vision Care, Inc.

Table 11: Power Calculations of NIBUT for N=54

Effect size ( $\Delta$ )	Common standard deviation ( $\sigma$ )		
	3	4	5
-2.1	81%	60%	45%
-1.1	38%	26%	20%
0.0	5%	5%	5%

The sample size is sufficiently large to demonstrate lower NIBUT with ~80% power to Symptomatic subjects if  $\Delta \leq -2.1$  and  $\sigma \leq 3$ .

3. Hypothesis 3: Symptomatic subjects will have, on average, lower TMH compared to asymptomatic subjects after 14 hours of lens wear.

Table 12: Power Calculations of TMH for N=54

Effect size ( $\Delta$ )	Common standard deviation ( $\sigma$ )		
	0.04	0.06	0.08
-0.04	98%	78%	56%
-0.03	86%	57%	39%
-0.01	23%	15%	12%

The sample size is sufficiently large to demonstrate lower TMH with ~80% power to Symptomatic subjects if  $\Delta \leq -0.03$  and  $\sigma < 0.06$ .

4. Hypothesis 4: Symptomatic subjects will have, on average, greater tear film osmolarity (TOSM) compared to asymptomatic subjects after 14 hours of lens wear.

Table 13: Power Calculations of TOSM for N=54

Effect size ( $\Delta$ )	Common standard deviation ( $\sigma$ )		
	20	25	30
10	57%	42%	33%
12	70%	54%	42%
14	81%	65%	52%

The sample size is sufficiently large to demonstrate greater TOSM with ~80% power to Symptomatic subjects if  $\Delta \geq 14$  and  $\sigma \leq 20$ .

5. Hypothesis 5: Symptomatic subjects will have, on average, greater mean number of white blood cells (WBC) (visualized by confocal microscopy) in both the upper and lower lid margins compared to asymptomatic subjects after 6 hours of lens wear.

Table 14: Power Calculations of WBC for N=54

Mean ratio ( $\phi$ )	Common coefficient of variances (CV)		
	0.65	1.0	1.3
1.0	5%	5%	5%

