# Clinical Study Protocol

## Johnson & Johnson Vision Care, Inc.

- Unstructured Covariance Structure (UN)
- Homogenous Compound symmetry (CS)

The structure that returns the lowest Akaike Information Criteria Corrected (AICC) will be selected as the structure that best fit the data. Heterogeneous covariance structures across strata may be considered if necessary. The Kenward and Roger method (Kenward and Roger, 1997) will be used for the denominator degree of freedom.

The Comparison between the symptomatic and the asymptomatic strata will be carried out using one-sided 95% confidence intervals for the Least-squares means risk ratio (symptomatic over asymptomatic) at 6-hour follow up for the hypothesis given below:

$$\begin{aligned} H_0: \mu_S / \mu_A &\leq 1 \\ H_A: \mu_S / \mu_A &> 1, \end{aligned}$$

where S=Symptomatic and A=Asymptomatic. Adjustments for multiple comparisons across lower and upper lid margins will be performed using a simulation method with alpha equal to 0.05 (Edwards and Berry, 1987). A statistically significantly greater density of WBC, on average, in both the upper and lower lid margins for symptomatic subjects compared to asymptomatic subjects after 6 hours of lens wear will be concluded if the multiple adjusted lower limit of the 95% confidence intervals for the Least-squares means risk ratio is above 1.0.

**Remark:** For all the above models, the Kenward and Roger method implemented with the *kr2* option in SAS will be used for the calculation of the denominator degrees of freedom. Heterogenous models across subject strata may be considered. The log-likelihood ratio test will be used to test for homogeneity between the two strata. Convergence limitations will be taken into account as necessary. If convergence is problematic, then reduced versions of the corresponding model will be considered. When the normality assumption does not hold for an endpoint, the analysis will be conducted on transformed data; generalized linear models or generalized linear mixed models with appropriate distributions will also be considered on the original data.

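### The white-cell endpoint is a density, but the primary Poisson model is written for a number of cells, with no stated allowance for how much lid was imaged

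*Combined protocol and SAP*

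**What the plan says.** **Density.** The synopsis lists the endpoint as "mean density of white blood cells". Section 2.2, under White Blood Cells, says of the confocal images: "These images will be used to determine the density of inflammatory white blood cells". Hypothesis 5 in section 2.3 predicts "greater density of white blood cells (visualized by confocal microscopy) in both the upper and lower lid margins" in symptomatic subjects. The decision sentence in section 14.5 concludes "A statistically significantly greater density of WBC, on average, in both the upper and lower lid margins".

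**Number.** The opening paragraph of section 2.2 says "the number of white blood cells in the lid margins after 6 hours of lens wear will be investigated". Section 14.2 restates hypothesis 5 as a mean number of cells. In section 7.2, steps 2.11 and 6.11, the output of image analysis is a number of cells. The primary model follows this second usage: "The number of white blood cells (visualized by confocal microscopy) after 6-hour follow up will be analyzed using a generalized linear mixed model". It has a Poisson distribution and log link, stratum as fixed effect, subject as random effect, age, gender and race where appropriate, and a residual covariance between lids. No offset, exposure or image-count term is stated, and nothing says how a number becomes a density.

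**Amount imaged.** Steps 2.11 and 6.11 say only: "A number of images will be undertaken across the central lid area". Appendix I (SOP #53) leaves the operator to select the field lens and the acquisition mode: a single section, a sequence of up to 100 images, or a volume of 40. It names 300 and 400 µm fields.

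**The concern.** A log-link model for a count estimates a ratio of expected counts. That is a ratio of densities only if the area searched is the same on average in both strata, or is in the model as an offset. Here the area is neither fixed nor modelled, yet the conclusion is worded as a density.

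The choice of analysed unit (total over images, average per image, or cells per unit area) decides what the stratum ratio means and whether a Poisson variance is reasonable. The plan leaves that choice open for one of its five primary measures. Section 14.7 repeats the same analysis for Part 2, and the white-cell variable also enters the correlations in sections 14.6 and 14.7.

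**Working it through.** **Inputs.** 27 subjects per stratum (section 14.2); one-sided 95% interval for the ratio (section 14.5); mean ratios and CVs from Table 14; historical means and SDs from Table 9. The documents give no image counts, so every imbalance below is an assumption.

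**1. Reproduce Table 14.** Use a t test on the log scale with σ = √ln(1 + CV²), noncentrality = ln(ratio) / (σ√(2/27)), 52 degrees of freedom and one-sided 5% (critical value 1.675). At CV 0.65, σ = 0.594. For ratio 1.5 the noncentrality is 0.405 / (0.594 × 0.272) = 2.51, giving 79.7% power against the 80% stated. All nine cells agree to within rounding. For ratio 1.5 the other two are 54.8% (stated 55%) and 43.4% (stated 43%). This calculation contains no imaged area and is not the planned Poisson model.

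**2. If totals are analysed.** Expected count = density × area imaged, so

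estimated ratio = density ratio × (symptomatic area / asymptomatic area).

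Take a true ratio of 1.5 and 20% fewer symptomatic images of equal field size: 1.5 × 0.80 = 1.20. Putting 1.20 into the step 1 formula gives:

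| CV | Power at 1.5 | Power at 1.20 |
|---|---|---|
| 0.65 | 80% | 30% |
| 1.0 | 55% | 20% |
| 1.3 | 43% | 16% |

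A simplified subject-level simulation was also run: overdispersed Poisson counts, subject-density CV 0.65, 27 per stratum, robust standard errors. With 20% fewer symptomatic images it gave a ratio of 1.20 and 23% power without an offset, against 1.50 and 67% with one. With equal mean imaging it gave 1.50 either way, with power 65% without and 70% with the offset.

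**3. Which unit do the historical data suggest?** Whole-number counts from N subjects have a whole-number sum, so mean × N should be an integer up to rounding (at most 27 × 0.0005 = 0.0135).

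- 3.044 × 27 = 82.19 and 4.130 × 27 = 111.51 are not integers.
- 9.301 × 15 = 139.52 is not an integer.
- 6.533 × 15 = 98.00 and 8.267 × 15 = 124.01 are, within rounding (here 0.0075).

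Fourteen of the 16 means fail the check, assuming that all N subjects contribute to every cell. This points to averages or densities.

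**4. If per-image averages are analysed.** Let a lid have density λ, m images and field area a. If the total is Poisson with mean λma, the average has mean λa and variance λa/m. The mean does not contain m, so image number does not shift the ratio. The variance is 1/m of the Poisson value and changes with m. Field area a stays in the mean: if 300 and 400 µm are square field widths, the area per image differs by (400/300)² = 1.78.

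**5. Which CV applies?** SD/mean in Table 9 is 0.64 in one cell (symptomatic, right lower lid, Visit 2) and 0.91 to 1.28 in the other 15.

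**The case against.** The strongest reply is that the endpoint label already speaks of a mean density and Table 9 looks like averages, so the sponsor probably intends a per-image quantity. A log-link mean model on averages still targets a ratio of means, and the specified residual covariance can absorb part of the variance misfit. Unequal image numbers would then mainly affect weighting and efficiency. Investigators are masked to stratum, so imaging effort should not be chosen by group. Section 14.1 also defers detail to a stand-alone SAP that is not in the supplied text, where an offset could appear.

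Much of this stands, and it rules out several stronger readings that a reader might infer:

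- **That the ratio necessarily moves with the amount of lid imaged.** It does so only if totals are analysed and imaging differs by stratum. Under averages, field size is the remaining route.
- **That symptomatic wearers will yield fewer usable images.** Section 1.4 lists temporary discomfort from lid manipulation and from the procedure, but the documents do not say that tolerance differs by stratum. Masking does not remove such a difference if it exists.
- **That the false-positive rate is inflated.** The formula gives 14% instead of 5% at CV 0.65 for 10% more symptomatic images and no true difference (10.9% at CV 1.0, 9.7% at CV 1.3). A tolerance problem would produce fewer images, which pulls the ratio down.
- **That a fall from 80% to 30% is the typical loss.** It uses a CV that only one historical cell approaches, and a single comparison without the planned adjustment across lids.

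The objection does not remove the gap. Section 14.5 states a specific model for a number of cells, with no exposure term, and draws a density conclusion from it. Neither reading of number makes that model and that conclusion agree as written.

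**Conclusion.** The concern holds in conditional form, and the plan should be changed. The endpoint, hypothesis 5 and the conclusion are a density; the model is for a number, with no offset stated and the amount imaged not fixed.

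The size depends on the unit. Under totals, the estimate is the density ratio times the ratio of area imaged. An assumed 20% shortfall in symptomatic images costs 50, 35 or 27 percentage points of single-comparison power at CV 0.65, 1.0 or 1.3. With equal mean imaging the cost is only some precision. Under per-image averages, which Table 9 favours, there is no shift from image number, but the response is not a count, the Poisson variance does not apply, and field size can still enter the ratio.

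The documents do not show that any imbalance will occur. What they establish is that the plan has no stated protection against one and does not define the quantity it analyses.

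**What to change.** In section 14.5, define the response as total cells per lid and eye, and add the offset log(number of analysed images × image field area) to the Poisson log-link model. The exponentiated stratum effect is then a density ratio, which matches hypothesis 5 and the decision sentence. Record the number of analysed images and the field area for each lid and eye at Visits 2 and 6. Use the same density in the Part 2 analysis and the correlations, and align the number wording in sections 2.2 and 14.2 with it.

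Fixing the number of images and the field lens in steps 2.11 and 6.11 would also help, but the offset still protects the analysis when images are lost.

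The cost is one or two data fields and one model option. No extra visit or procedure is needed, because the images are already taken and analysed.

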# Clinical Study Protocol

## Johnson & Johnson Vision Care, Inc.

- Unstructured Covariance Structure (UN)
- Homogenous Compound symmetry (CS)

The structure that returns the lowest Akaike Information Criteria Corrected (AICC) will be selected as the structure that best fit the data. Heterogeneous covariance structures across strata may be considered if necessary. The Kenward and Roger method (Kenward and Roger, 1997) will be used for the denominator degree of freedom.

The Comparison between the symptomatic and the asymptomatic strata will be carried out using one-sided 95% confidence intervals for the Least-squares means risk ratio (symptomatic over asymptomatic) at 6-hour follow up for the hypothesis given below:

$$\begin{aligned} H_0: \mu_S / \mu_A &\leq 1 \\ H_A: \mu_S / \mu_A &> 1, \end{aligned}$$

where S=Symptomatic and A=Asymptomatic. Adjustments for multiple comparisons across lower and upper lid margins will be performed using a simulation method with alpha equal to 0.05 (Edwards and Berry, 1987). A statistically significantly greater density of WBC, on average, in both the upper and lower lid margins for symptomatic subjects compared to asymptomatic subjects after 6 hours of lens wear will be concluded if the multiple adjusted lower limit of the 95% confidence intervals for the Least-squares means risk ratio is above 1.0.

**Remark:** For all the above models, the Kenward and Roger method implemented with the *kr2* option in SAS will be used for the calculation of the denominator degrees of freedom. Heterogenous models across subject strata may be considered. The log-likelihood ratio test will be used to test for homogeneity between the two strata. Convergence limitations will be taken into account as necessary. If convergence is problematic, then reduced versions of the corresponding model will be considered. When the normality assumption does not hold for an endpoint, the analysis will be conducted on transformed data; generalized linear models or generalized linear mixed models with appropriate distributions will also be considered on the original data.

